After enrollment into the study, participants will be randomly allocated to either the placebo nail solution or the active topical nail solution. Randomization will be carried out by means of electronic random number generation under the authority of a co-investigator ([name]), who will prepare sealed, sequentially numbered envelopes for each study site, and mail the envelopes to the designated coordinator for each study site (A-J) (Table 1). In each sealed envelope will be a tube of the topical solution, either the active topical nail solution or the placebo nail solution, consistent with the random number list, which will determine whether or not the placebo or active topical nail solution is contained in the tube. Each tube will be numbered in sequential numeric order from 1 to n, and recorded in the investigator's master list, which will serve to record the random allocation code, detailing whether or not the placebo nail solution or the active topical nail solution was dispensed in the designated tube. Furthermore, each block of tubes will be designated with a letter, A to J, to represent the distinct study sites. The labeled tubes will be mailed to the study sites in blocks of 10, and replenished based on the prevalence of enrolment at each site. At each study site, the investigator will open, in sequential numeric order, a sealed envelope and dispense the labeled tube to the eligible participant in consecutive order. Neither the study doctors responsible for assessing the results of the intervention, nor the participants themselves, will know which of the treatment groups the participant will be in (until after completion of the analyses, when the randomization code will be revealed if a participant or investigator desires to know, and participants randomized to the placebo group will also have the opportunity to receive, from the study sponsor, and free of charge, a course of the active topical nail solution with the Tolcylen™ Fungal Eradication Nail/Skin Renewal Kit, which includes Tolcylen™ Antifungal/Nail Renewal Solution, Tolcylen[™] Antifungal Skin Cream, and Tolcylen[™] Antimicrobial Shoe Spray (up

CONFIDENTIAL

to 2 kits)). The nail solution with its envelope will be stored in a secure medicine supply cabinet or at the site investigator's office at a secure location.

Diagnosis of Primary Outcome

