The clinical disease under evaluation is pedal onychomycosis. Onychomycosis will be confirmed if fungal hyphae are observed on periodic acid-Schiff (PAS) stain examination of nail plate/bed tissue fragments. The fungal cell wall is composed of layers of chitin, glucan mannoproteins, and glycosylphosphatidylinositol, and the periodic acid-Schiff reaction colors these polysaccharides in the cell walls of fungi magenta. PAS staining of nail clippings is more sensitive than potassium hydroxide (KOH) and fungal culture for the diagnosis of onychomycosis (56). The PAS stain examination will be conducted by a certified microbiology laboratory of the site investigator's choice (their usual and customary practice) or an independent lab that has contracted with the sponsor to conduct the PAS test in support of the investigation. Each site investigator, or the contracted microbiology lab, will forward the results of the PAS tests for each participant. The payment for the baseline PAS stain will be handled by the patient's insurance, in the usual and customary fashion, since this is the typical requirement for standard treatment of mycotic toenails. Once again, anyone randomized to placebo nail solution will receive the active topical nail solution, Tolcylen[™], at the end of the treatment as described elsewhere in this protocol, if the participant desires. The PAS stain examination will be repeated at the termination of the intervention period, at either 3, 7 or 9 months after initiation of the intervention, and will be collected for the purposes of the investigation. As such, PAS assessments after the baseline test are not necessarily part of the clinician's usual and customary practice, since standard therapy usually does not entail a second mycology assessment if therapy has been successful. If, however, nail dystrophy persists, then a follow up PAS stain would be considered a reasonable component of standard therapy. To be fair to our participants, the cost of this final PAS assessment will be covered by the study sponsor. We will also randomly allocate a number of participants to either the active or placebo topical solution even if they do not have a PAS stain positive for fungal elements at baseline, in an effort to ascertain the influence that the active solution might have on non-mycotic dystrophic toenails. The investigation will not be powered a priori to see a statistically significant difference in this secondary analysis.

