Study Product, Dose, Route and Regimen

All participants will be undergoing one of two interventions. Participants in the control group will apply the placebo nail solution to the involved toenail/s. Preparation of the placebo nail solution (dimethicone 5%, a skin protectant and emollient) was undertaken with the aim of making it as close as possible to the active treatment agent in terms of color and texture, and the gross physical

CONFIDENTIAL

Efficacy of Topical Active Nail Solution versus Placebo Nail Solution Alone Principal Investigator: [name], DPM Sponsor: Marlinz Pharma

appearance of the solution. The placebo nail solution, like the active topical nail solution, meets the FDA's safe ingredient criteria for an over-the-counter topical agent. The placebo nail solution, like the active topical nail solution, will be supplied in three (3) 7.5 ml tubes with a controlled-release applicator mechanism that allows thin coat of the solution to be applied at a time, and the instructions for application specify that only thin coat of solution to be applied daily to under the leading edge, borders of the toenail and the entire surface of the toenail. It is expected that use of the controlled-release applicator tube will last on average 4 to 5 months when used on two toenails, and therefore each participant will be provided with three (3) tubes of the randomly allocated solution as needed during each follow up visit of their participation in the investigation. The tube containing the topical solution is also designed to prevent evaporation of the agent, and the base terminal of the tube will have a crimped seal labeled with an imprinted code that designates the ingredient as either placebo or active topical solution contained in the tube. Three tubes will be dispensed in order to provide enough of the randomly allocated solution to minimize the potential need to supply more product. If a tube is lost by the participant, or if for any reason the participant runs out of the randomly allocated topical solution, then the PI will ascertain the precise agent (placebo or active topical nail solution) and a replacement tube (also with the base terminal of the tube labeled with an imprinted code that designates the ingredient contained in the tube as either placebo or active topical solution) of the randomly allocated topical solution will be forwarded directly to the study site and dispensed to the participant.

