A visible nail plate involvement score (Table 3, below) will be used to assess the clinical appearance of an involved toenail, at baseline and then repeated at each follow up visit. This score was designed to provide a continuous numeric value to rate the gross clinical appearance of dystrophic and/or mycotic toenails. The score ranges from a low of 7 to a maximum of 27, with a lower score indicative of a more normal appearing toenail and a higher score indicative of more advanced toenail dystrophy based on gross clinical inspection. This scoring scale was deemed reliable when tested for inter- and intra-rater reliability; wherein, 4 observers rated 40 nails on two separate occasions 3 weeks apart (Pearson's product-moment correlation coefficients for inter-rater reliability ranged from

CONFIDENTIAL

0.8849 to 0.9609 and the intra-rater reliability ranged from 0.8768 to 0.9687). Pearson's product-moment correlation coefficients range from -1 (100% negative association, or perfect inversion) to +1 (100% positive association, or perfect agreement), with a value of zero indicative of the absence of an association. In general, correlation coefficients with absolute values ranging from 0.60 to 1.00 are considered strong, and those <0.40 are considered weak. Our assessment of this scoring scale for visible toenail involvement indicated strong positive agreements for between and within rater correlations. The index toenail will be rated either by the blind site investigator, or submitted as a photograph for blind study coinvestigators to score. A decrease in the VNPIS of \geq 60% at any follow up visit will be considered a clinical cure.

	/	
Nail plate characteristics		Point/s
Type of apparent onychomycosis [select one]	White superficial	1
	Distal subungual	2
	Proximal subungual	3
	Any combination of above	4
Longitudinal segmental involvement of visible nail	≤ Distal half	2
plate (location of gross visible nail plate	> Distal half, excluding lunula	3
involvement) [select one]	Extending proximal to lunula	4
Apparent percentage involvement of visible nail	≤ 25%	2
plate [select one]	> 25% ≤ 50%	3
	> 50% ≤ 75%	4
	> 75%	5
Overt gross appearance of involved nail. For	Overtly thickened nail plate	2
thickness, inspect distal margin of visible nail plate	Lytic, overtly lifted from nail bed	3
and bed (including hyperkeratosis of nail bed	Onychauxis, gryphosis,	1
attached to plantar surface of nail plate) compared	clubbed, ram's horn shape	4

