This information will remain only with these two individuals, the coinvestigator ([name]) and the science officer, or his/her direct appointee assigned to this task and will not be accessible to any clinical researchers employed at Marlinz Pharma. Moreover, the secured information will not be available to investigators or participating clinical sites during the extent of the investigation, with the exception of the member of the investigational team responsible for assuring that participants are assigned to the appropriate treatment group (in accordance with the randomized allocation schedule), namely the coinvestigator ([name]). In the event of an emergency, the investigators may contact:

[name], DPM [name] Penn Presbyterian Medical Center [name] [contact]

[name] Marlinz Pharma [name] [contact]

If there is a need to obtain the Blind Schedule, prior authorization will be required. The decode procedure for blinding will be strictly adhered to. Unblinding will be documented in the source documents and CRFs, and notification of the sponsor will take place within 24 hours by Email, text

CONFIDENTIAL

message or telephone or telefax, followed by a written narrative of the event within 48 hours.

Data and Safety Monitor (DSM)

This study will be monitored by a Data and Safety Monitor, should any adverse or serious adverse events arise. The details of the organization and operation of the DSM are described in Attachment 9, appended to this protocol.

Stopping Rules

It is not anticipated that this study will impart a high or unreasonable risk to the participants. Nonetheless, a Data Safety Monitor (DSM) will have oversight of the progress and make recommendations related to participant safety and progress. The DSM will have the authority to dictate stopping rules, based on his/her analysis of the results of the study at predetermined times along the course of the investigation. The details of the organization and operation of this DSM are described in Attachment 9, appended to this protocol.

Medical Monitoring

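### Tubes handled by participants and possible raters carry a code for their ingredient, and the protocol does not say that it is masked or unique to each tube

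*Protocol*

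**What the plan says.** Under Study Product, Dose, Route and Regimen, the base of each tube has a "crimped seal labeled with an imprinted code that designates the ingredient as either placebo or active topical solution contained in the tube". The same section says that a replacement for a lost or exhausted tube is "also with the base terminal of the tube labeled with an imprinted code that designates the ingredient contained in the tube". For such replacements the principal investigator (PI) finds out which agent the participant is on, and the tube goes to the site.

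Under Method for Assigning Participants to Treatment Groups, each tube also has a sequential number and a site letter. These are entered in a master list "which will serve to record the random allocation code". At the site, "the investigator will open, in sequential numeric order, a sealed envelope and dispense the labeled tube to the eligible participant in consecutive order". The same section undertakes that neither the assessing doctors nor the participants will know the group until the analyses are complete.

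On assessment, the VNPIS section says: "The index toenail will be rated either by the blind site investigator, or submitted as a photograph for blind study coinvestigators to score". For the primary endpoint, Diagnosis of Primary Outcome says: "The PAS stain examination will be conducted by a certified microbiology laboratory of the site investigator's choice", or by an independent laboratory contracted by the sponsor.

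Unblinding Procedures keeps the allocation list with the allocation co-investigator and the sponsor's science officer, and away from other investigators and the sites. It adds: "If there is a need to obtain the Blind Schedule, prior authorization will be required".

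**The concern.** A mark whose stated purpose is to show whether a tube holds placebo or active sits on an object that the site investigator hands over and the participant uses daily for up to 9 months. The protocol otherwise takes care over blinding, with matched colour and texture, identical applicators and a restricted allocation list. Yet it does not say that this mark is covered, that it differs from tube to tube, or that raters are kept away from it.

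If the mark is the same on every tube of one arm, anyone who sees several tubes can sort participants into two groups, and learning the content of one tube labels both groups. The outcomes most open to such knowledge are the two secondary endpoints (the VNPIS when the site rates it, and the self-reported OnyCOE-t), together with the site's decisions on stopping early and on collecting nail specimens.

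**Working it through.** The issue is mainly one of reading the sections together. The arithmetic only bounds its size.

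**1. Number of participants at stake.** The plan's own figure reproduces: 2 × 29 = 58, and 58 × 1.2 = 69.6, rounded up to 70. There are nine sites (A to H, and J), so the average is 70 / 9 = 7.8, about 8 per site.

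**2. One mark or two?** The assignment section describes a sequential number and site letter that identify the tube and need the master list to decode. The product section describes a code that identifies the ingredient. The functions differ, and replacement tubes also carry the second mark, with no new tube number mentioned. This fits a product mark shared by all tubes of an arm better than a tube-specific code. The wording does not settle it.

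**3. What one decoded tube reveals.**

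| Nature of the imprinted code | Arms revealed by one decode |
|---|---|
| Unique to each tube, read through the master list | 1 participant |
| Shared by arm | Every tube the person sees: about 8 participants at an average site, at most all 70 |

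**4. Would a site see both codes?** This step assumes a shared code, independent 1:1 allocation and n participants at the site. The probability that both arms are present is 1 − 2 × 0.5^n.
- n = 8: 1 − 2 × 0.0039 = 0.992
- n = 4: 1 − 2 × 0.0625 = 0.875

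The protocol fixes no enrollment per site, so both values of n are assumptions. The result means only that most sites could form two groups. It does not tell them which group is active.

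**5. How could a decode arise?** The protocol supplies one ordinary route. The PI is listed as the Site E investigator and also identifies the agent whenever a replacement is needed. A replacement for a Site E participant would put the agent and the code before the same enrolling investigator. This also contradicts Unblinding Procedures, which withholds that information from every investigator except the allocation co-investigator. The note to Table 1 points the same way as the replacement rule, because it has the PI track active and placebo distribution. This contradiction does not depend on what the code looks like.

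**6. Which outcomes are reached?**
- VNPIS scored at the site: exposed, if the rater has handled or seen the tube.
- VNPIS scored from photographs: not directly exposed.
- OnyCOE-t: exposed, because the participant holds the tube.
- PAS reading: done in a laboratory, not directly exposed.
- PAS specimen collection and its timing at 3, 7 or 9 months: handled at the site, so indirectly exposed. Stopping early depends partly on clinical evidence of cure.

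**The case against.** The strongest reply is that a tube-specific code looked up on the master list also designates an ingredient, and the assignment section describes just such a system. The imprint could be the same site-tube number, loosely described. That cannot be excluded. A reader might infer that one decoded or guessed tube unblinds the whole trial, but the protocol never says that the code is shared by arm, so that holds only as the upper end of the range.

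Four further points stand:
- The protocol does not say that the dispensing investigator and the rater are always the same person, and it offers scoring from photographs as an alternative.
- That participants and raters notice the code is an inference from where it is printed.
- The primary endpoint is read by a laboratory, and nothing suggests that the laboratory sees tubes.
- Emergency unblinding is a remote route. The protocol expects knowledge of the arm to make no difference to management, and it requires prior authorization.

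A reader might also try to size a bias in PAS by giving each arm one end of the 61% to 98% sensitivity range quoted in Review of the Literature. The document does not support this. That range describes the stain. The separate remark that yield depends on where the specimen is taken rests on another source and has no figures. Nothing ties tube codes to a difference in sampling of any size.

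What the reply does not meet is the silence on masking and uniqueness, or the PI's role in replacements.

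**Conclusion.** The point holds as a weakness in the protection of blinding. An ingredient-designating code is placed on original and replacement tubes that pass through the hands of participants and possible raters, with no statement that it is masked or unique to each tube. This does not fit the blinding promised in the assignment section or the restricted access in Unblinding Procedures.

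One decode exposes between 1 participant and all 70. The upper end requires a code shared by arm and someone who sees tubes from all sites. A shared code is the more natural reading but not a stated one. The effect falls mainly on secondary endpoints and site decisions. It reaches PAS only through specimen collection and timing, and no size can be given for that. The conflict over who identifies the agent for replacements is firm under either reading.

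**What to change.** - In both places in Study Product, Dose, Route and Regimen, delete the ingredient code, or state that it is over-labelled before shipment.
- Identify every tube, including replacements, only by a unique site-tube number. Keep the link from number to product solely on the allocation co-investigator's master list, with the sponsor's secured copy as Unblinding Procedures describes.
- Have the allocation co-investigator, not the PI, identify the agent when a replacement is needed. Amend the note to Table 1 so that it agrees with Unblinding Procedures.

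The cost is a label change, or over-labelling of stock already crimped, and a short text amendment. Traceability is kept, because the tube number and master list already provide it. The change is sound under either reading: it removes a shared code if there is one, and corrects a misleading description if there is not.

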The recruitment and screening period for potential participants will be 12 months (in order to identify 70 eligible participants) following the decision to initiate the protocol. It is expected that 70 participants will be informed and consented, and enrolled in the study, by approximately 12 months. Treatment for each participant will be carried out for a total of 9 months, or less if there is evidence of clinical

CONFIDENTIAL

and mycological cure prior to that time. The 9-month follow up visit will serve as the primary efficacy endpoint, in keeping with the usual expected minimum 7 to 9 -month duration of time expected for a full replacement of the visible nail plate in a typical adult human. Thereafter, a 3-month period will be allotted for completion of mycological testing and data collection. An additional 3 months will be allotted for completion of the analyses and 3 more months to write the report describing the study and submission of the manuscript for consideration for publication in a refereed journal. It is, therefore, estimated that the duration of time necessary for the completion of this protocol, data analysis, and preparation of the final report, will be approximately 35 months.

Study Centers

This study will be carried out at multiple clinical offices, under the guidance of different CITI-trained investigators, including:

- [name], DPM; Ankle & Foot Associates, [contact] (cell) Contact: Self; [contact], [name]. Site A
- [name], DPM; St Cloud Foot & Ankle; [contact] (cell) Contact: self; [contact] [name]. Site B
- [name], DPM; National Foot and Ankle, [contact] (cell) Contact: Self; [contact], [name]. Site C
- 4. [name], DPM; Family Foot Care, [contact] (cell) Contact: Self; [contact], [name]. Site D
- [name], DPM (the Principal Investigator); Foot & Ankle Specialists of Nevada, [contact] (cell) Contact: Self; [contact], [name]. Site E
- [name], DPM; A Step Ahead Foot and Ankle, [contact] (cell) Contact: Self; [contact], [name]. Site F
- [name], DPM, [name], DPM; The Division of Podiatry at The GW Medical Faculty Associates, [contact]) Contact: Office; [name]. Site G.

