Table 1 Topical solution tube site-participant designation*

CONFIDENTIAL

A4	B4	C4	D4	E4	F4	G4	H4	J4
A5	B5	C5	D5	E5	F5	G5	H5	J5
A6	B6	C6	D6	E6	F6	G6	H6	J6
A7	B7	C7	D7	E7	F7	G7	H7	J7
A8	B8	C8	D8	E8	F8	G8	H8	J8
A9	B9	С9	D9	E9	F9	G9	H9	J9
A10	B10	C10	D10	E10	F10	G10	H10	J10
An	Bn	Cn	Dn	En	Fn	Gn	Hn	Jn

*This designation correlates with the randomization schedule and enables the principal investigator to keep track of active and placebo distribution and use.

A study coinvestigator, not participating at a study site, and not tasked with data analyses, will maintain the random allocation code, which will contain this same information as well as the randomly allocated topical solution, denoted as either the placebo nail solution or the active topical nail solution.

Inclusion and Exclusion Criteria

Inclusion criteria for participation in this study include:

- 1. Male or female participants aged 18 years or older;
- 2. If female is of childbearing potential, she must not be pregnant at the time of enrollment and she must be using an accepted form of birth control during the study treatment period (acceptable forms include: postmenopausal, surgical sterility, complete abstinence, sterilized sexual partner, tubal occlusion, copper-T intrauterine device, levonorgestrelreleasing intrauterine device, medroxyprogesterone injections, etonogestrel implants, combined pills, norelgestromin/ethinly estradiol transdermal system, intravaginal device, or Cerazette pill; and for males the use of a condom with spermicide or surgical sterility);
- 3. Participant has a diagnosis of onychomycosis diagnosed by means of history, physical examination, and positive (evidence of fungal hyphae) mycological tissue examination by periodic acid-Schiff (PAS) staining;
- 4. At least one toe nail with distal subungual involvement, localized to any toe, with at least 10% involvement and including up to 100% involvement of the visible nail plate, any nail plate thickness, with the index nail being the most involved per inspection by the on-site investigator and agreed upon by the designated co-investigator study doctor ([name], DPM), who will inspect specific clinical photographs of the involved nail/s (the photographs will be obtained at each study site using a specified method, as demonstrated to site investigators, so that the clinical features are appropriately demonstrated);

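### The Principal Investigator, who is the listed Site E investigator, learns the assigned agent whenever a tube must be replaced, contrary to the protocol's own limits on access to the allocation code

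*Protocol*

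**What the plan says.** Who may know the allocation:

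- Study Summary (Statistical Methodology) says that participants, all observers and outcomes assessors are blind.
- Method for Assigning Participants to Treatment Groups: "Neither the study doctors responsible for assessing the results of the intervention, nor the participants themselves, will know" the assigned group until the analyses are complete.
- Study Population (text after Table 1) places the random allocation code with a coinvestigator who works at no study site and does not analyse the data.
- Unblinding Procedures keeps the schedule from investigators and sites throughout the trial. Within the investigational team, that one coinvestigator is the only exception.

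What points the other way:

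- Study Product, Dose, Route and Regimen sets the trigger, "If a tube is lost by the participant, or if for any reason the participant runs out of the randomly allocated topical solution", and the consequence, "then the PI will ascertain the precise agent (placebo or active topical nail solution) and a replacement tube" is forwarded to the site.
- The Table 1 footnote says that the site-participant designation "enables the principal investigator to keep track of active and placebo distribution and use".
- Study Centers lists the PI as the investigator for Site E and names no other investigator there.

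Two related statements:

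- Each tube, original or replacement, bears "an imprinted code that designates the ingredient as either placebo or active topical solution contained in the tube".
- Diagnosis of Primary Outcome says that "anyone randomized to placebo nail solution will receive the active topical nail solution" at the end of treatment, if desired, and refers to the description given elsewhere in the protocol.

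**The concern.** The trial is presented as placebo-controlled with blinded outcome assessors, and much of what it measures involves judgement. A site investigator who knows the arm can, without intending to, score a nail more favourably, sample a different part of it, or judge clearance sooner. The protocol's own literature review says that different specimen layers give different rates of fungal confirmation, and the final PAS sample may be taken at 3, 7 or 9 months depending on when the intervention ends. Sampling and timing are therefore routes by which knowledge of the arm could reach even a laboratory-read endpoint. Once the blind is lost it cannot be restored, and no analysis could show that scoring at the affected site was untouched.

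**Working it through.** The protocol gives no figure for this point. The check is mainly a comparison of passages, with two small calculations for scale.

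**1. Can the access rules all be followed?** Unblinding Procedures excludes investigators, with one coinvestigator excepted. Study Population says that this person is not at a study site. The PI is the listed investigator at Site E and so is not that person. The replacement procedure nevertheless has the PI establish the agent. The PI does share responsibility with the sponsor for any necessary unblinding, but that provision covers a need to unblind, requires prior authorisation and calls for documentation. Replacing a tube is routine supply. The passages cannot all be followed as written.

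**2. What could the PI influence at Site E?** The VNPIS section lets the blind site investigator rate the index nail, or lets blind coinvestigators score a photograph. At Site E the only listed site investigator is the PI, and the photograph route is an alternative, not a requirement. No passage names the PI as rater or as sampler; both roles are inferred from the Site E listing.

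**3. Is the primary endpoint reading exposed?** The PAS stain is read by a laboratory chosen by the site or contracted by the sponsor. No passage gives that laboratory the allocation. The reading itself is not shown to be affected; only sampling and its timing could be.

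**4. How often might a replacement be needed?** Inputs from the study product section: a tube lasts 4 to 5 months on two nails; three tubes are supplied; treatment lasts up to 9 months.

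- Per tube: 2 × 4 = 8 to 2 × 5 = 10 nail-months.
- Three tubes: 3 × 8 = 24 to 3 × 10 = 30 nail-months.
- Nails covered for 9 months: 24 / 9 = 2.7 to 30 / 9 = 3.3.
- Three nails need 27 nail-months: 27 / 10 = 2.7 to 27 / 8 = 3.4 tubes.
- Four nails need 36 nail-months: 36 / 10 = 3.6 to 36 / 8 = 4.5 tubes.

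The inclusion criteria set no upper limit on the number of nails. If three tubes are the whole supply, a participant treating four nails for the full period runs out. The same section can also be read as supplying tubes as needed at each follow-up visit, which would make running out rarer. The frequency cannot be fixed from the protocol; it need not be negligible.

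**5. How many participants?** Nine sites (A to H and J) and 70 participants give 70 / 9 = 7.8, about 8 at Site E, assuming even enrolment. That is the ceiling at Site E if the footnote means arm-level access. Under the replacement step alone, the number is the unknown subset of these who need a tube. For a replacement at another site the PI also learns the arm, but no passage gives the PI an assessment role there.

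**6. When could an arm be disclosed?** In Table 2, enrolment runs to month 12, last visits to month 21 and analysis to month 27. A participant who starts at month 0 finishes at month 9, which is 21 − 9 = 12 months before the last visits. An offer of active product made at that point would disclose the arm during the trial; an offer made after the analyses would not.

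**The case against.** The strongest reply is that the conflict is narrow and most of the blinding stands. Much of that is right.

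- **Primary endpoint.** A laboratory reads the PAS stain, and nothing gives it the allocation. This stands.
- **PI as assessor.** The protocol calls for a blinded investigator at follow-up visits and allows photograph scoring by blind coinvestigators. No text says that the PI rates or samples. This stands as a limit, but with no other investigator listed at Site E the inference is reasonable.
- **Table 1 footnote.** The sentence after it says that the off-site coinvestigator's code holds the same information plus the allocated solution, which suggests that the designation list alone does not show the arm. The footnote is ambiguous, so access to every Site E allocation is not established.
- **Tube code.** A reader might infer that the imprinted code already unblinds everyone who handles a tube, or that one disclosure would expose all participants at all nine sites. The protocol does not say whether the code can be interpreted by sites or participants, or whether it is shared within an arm. That reading depends on an unstated assumption.
- **Early disclosure.** A reader might infer that placebo participants are told their arm when their own treatment ends. The sentence defers to the description elsewhere, and the section on assigning participants makes the offer after the analyses. This is at most an ambiguity of wording.

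None of this answers the replacement step. Supplying three tubes is meant to make replacement uncommon, but it does not change who learns the agent when replacement happens.

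**Conclusion.** The concern holds in a limited form. The replacement procedure gives the PI, who is the listed Site E investigator, the identity of the agent. This contradicts the restriction in Unblinding Procedures and the off-site code holder in Study Population, and it is incompatible with the blinding statements if the PI assesses participants at Site E. The exposure is to VNPIS rating, nail sampling and early-clearance judgement for Site E participants who need a replacement. The number is not stated; it rises to about 8 of 70 only if sites enrol evenly and the footnote means arm-level access. That the PI assesses at Site E is an inference from the site listing. The protocol does not support a conclusion that blinding fails across the trial or that the PAS reading is compromised. A tube code shared within an arm would let one unblinding reveal others, but that is a risk to be closed off, not an established fact.

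**What to change.** 1. In Study Product, Dose, Route and Regimen and in the Table 1 footnote, replace the PI with the off-site coinvestigator who already holds the code. That person looks up the allocation and arranges the replacement; the PI and the sites receive only a coded tube.
2. As a safeguard, state that the imprinted code is unique to each tube, carries no arm-level pattern and can be decoded only from the master list.
3. Align the sentence in Diagnosis of Primary Outcome with Method for Assigning Participants to Treatment Groups, so that the arm is not disclosed before the analyses are complete.

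The first change moves one task to someone already in the role. The second is a sentence, plus a change to the label print run if the present codes follow the arm. The third is wording only; if any site has been making the offer when a participant's own treatment ends, placebo participants would wait longer for it.
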